## **Confidentiality**

Participation in research may involve a potential loss of privacy. All records and documents pertaining to participation in this study will be handled as confidentially as possible. However, absolute confidentiality cannot be guaranteed.

All information, if collected on paper, will be kept in areas of limited access available to approved site study personnel only. Any physical records will be maintained in locked cabinets in locked offices, until the appropriate time at which documents may be shredded. Access to these cabinets will be limited to the study team.

Electronic data will be password protected and securely stored. The servers maintained by Posit Science are HIPAA compliant, secure servers that will require permissions from the study team to access.

Absolute confidentiality in group sessions is difficult to achieve irrespective of the delivery method (in-person, video-conference, etc.), as there is no guarantee that other group members will maintain confidentiality about sensitive information. However, in order to decrease the likelihood of breaches of confidentiality among group members, we will 1) provide informed consent about confidentiality; 2) educate group members about confidentiality; and 3) make the discussion of confidentiality an ongoing process.

- First, study participants will learn about confidentiality during the informed consent process. The consent form will clearly describe the roles and responsibilities of all parties and the limits of confidentiality.
- Second, individual sessions will be held between the site study coordinator and/or PEERS clinician and each participant to educate them regarding confidentiality prior to entering the intervention. Participants will be informed that 1) they have the right to choose an alias rather than their first name and decide at any point what information they choose to disclose; 2) the PEERS clinician will respect the patients' ability to choose what they disclose, and keep the promises of faithfulness and loyalty to all participants, including not revealing information participants disclose; 3) the PEERS clinician cannot promise that other group members will maintain confidentiality; 4) the PEERS clinician may have a legal obligation to break confidentiality in certain circumstances (e.g., child abuse), and those circumstances will be fully explained. The PEERS clinician will follow established procedures appropriate for their local jurisdiction to report such knowledge; 5) the research teams will be monitoring the Zoom contents, including chat history, throughout the intervention and as such any volunteered information that may be personally identifying will be available to research study monitors.
- Third, participants will be asked to read, sign and agree to be bound by a modified version of the American Psychological Association procedures and guidelines for group therapy (<http://www.apadivisions.org/division-49/publications/newsletter/group-psychologist/2011/04/group-procedures.aspx>), adapted for the target population, while in the intervention.
- Finally, during the first group session, the PEERS clinician will encourage group members to embrace the concept of confidentiality, making it their own rather than a mandatory rule.

Given that one of the goals of CICADAS is to enhance social functioning in individuals with ASD, we will not discourage group members from sharing contact information and befriending other study participants. Research shows that peer-to-peer interactions occur

naturally on social media platforms and serve many purposes, such as establishing new relationships, maintaining relationships, reconnecting with people, disclosing personal experiences of living with ASD, seeking and sharing information related to symptoms and medications.

Representatives of the Sponsor, the reviewing Institutional Review Board, and the National Institute of Health will be permitted to audit study-related data and related materials. Personally identifiable information will not be used in any study reports or publications; data contained in these will only be presented or published in aggregate form.

### **Disposition of Data**

The following study records will be retained by the site for minimum of two years following the conclusion of the study:

1. signed participant informed consent forms,
2. patient medical records, including all significant diagnostic reports,
3. supporting documentation of all adverse events,
4. completed eCRFs, and;
5. study related correspondence and study reports.

Paper records from this study must be stored in locked areas of limited access. During remote procedures, documents will be stored by the respective study personnel in a safe location with limited access until the documents can be shred or transferred to the Study Site. Electronic data must be securely held with restricted access available to personnel on a need-to-know basis only. Google Team Drive access will be restricted to authorized study personnel by invitation only.

### **Sharing Research Results**

Overall study results will be available to participants through ClinicalTrials.gov and when such results are completed and accepted for publication. At enrollment, information is collected that, if appropriate, we will share with the participant to ensure they are receiving appropriate health care (i.e. suicidality) as assessed by the C-SSRS. Any participant presenting a safety concern for any of these medical issues will be referred to ensure they are receiving appropriate treatment. We do not intend to share individual assessment data with participants, as the assessment battery is not intended to be the type of comprehensive battery a rehabilitation psychologist would use to guide treatment. Any participant interested in such comprehensive assessment will be referred to an appropriate clinician.

## Foreseeable Risks, Risk Management & Emergency Response

Participation in the study presents minimal risk. The probability and magnitude of harm or discomfort anticipated in this research study are not greater than those ordinarily encountered in daily life or during the performance of routine physical or psychological examinations or tests.

Serious adverse effects from prior studies of the treatments under study have not been reported. The protocol details potential risks related to study participation and includes assessments of increased risk of suicidality.

The following foreseeable risks will be discussed with potential participants during the enrollment visit, as will the following measures taken to minimize such risks:

- *Diagnostic interview and self-report measures.* Participants may feel uncomfortable or embarrassed due to sensitive questioning about their psychiatric condition and medical history during the diagnostic interview or on self-report measures. Participants will be reminded during each appointment that their participation in the study is voluntary and that as such, they are not required to complete any assessments and may skip individual questions or assessments entirely.
- *Discomfort During Assessments:* Assessments may be fatiguing for some individuals, particularly for those with persistent cognitive symptoms. To minimize this potential discomfort, breaks are encouraged and scheduled within the session. In the event that a participant appears to be under undue strain, test sessions are discontinued.
- *Lack of Assessment Feedback:* Participation in this study does not include feedback to participants on their individual assessment results. Though participants are informed of this policy during consent, some participants may find the lack of feedback to be frustrating.
- *Discomfort During Intervention/Program Use:* The following risks may be reasonably anticipated as the result of intervention and/or program use: fatigue, mood complaint, headache, tremor, eye strain, neck/shoulder discomfort, leg/hip discomfort, arm/wrist discomfort, back discomfort, headache and sleep difficulty. To minimize the fatigue participants are encouraged to sit ergonomically correctly while completing study activities on their device. The program is also designed to be entertaining and enjoyable. In addition, assessment and self-report sessions may be paused at any time and participants are encouraged to take breaks.
- *Other Risks:* Although it has not been previously documented, it is possible that the use of the investigational program or participation in the study activities may cause symptoms to worsen. There may also be risks related to the use of the program that are unknown at this time.

- *Loss of Privacy:* The most significant risk to the participants are those that would follow a breach of confidentiality and the disclosure of clinical information. Participation in any research study, including this one, may involve a loss of privacy, and absolute confidentiality cannot be guaranteed. Procedures designed to maintain data confidentiality include (1) formal protocol training sessions for all study team members emphasizing the importance of confidentiality, (2) adherence to specific procedures developed to protect participants' confidentiality, and (3) formal mechanisms limiting access to information that can link data to individual participants. One reason for breaking confidentiality is that the study personnel are required by law to report cases of physical or sexual abuse to local law authorities; and another is that despite all procedures, an error may occur. To mitigate this risk, data forms that include identifying information, with the exception of dates assessments are completed, date of birth, and dates associated with other data collected, and personally identifying information volunteered by participants in the Zoom chat forum, will be kept in locked cabinets or secure servers at the site, and accessible only to authorized study personnel. Only the unique ID number, assigned by the study coordinator, will represent participants during participation in the study. In the Zoom platform, participants will have the choice to self-identify with their first name or an alias. To facilitate tracking, a password-protected computer file will be maintained containing the identity of participants, their ID numbers, and contact information. This file, however, will contain no clinical data. Electronic data will be password protected and stored on a secure network. All data keys will be stored separately and securely. Only study personnel will have access to the study data. No participant names will be used in study reports or publications.
- *Risks of Email Communication:* This study will rely on the use of email communication between study personnel and research participants as part of their participation in the intervention. Site study personnel may be expected to email participants about their upcoming appointments, provide weekly updates on program usage, or communicate other important study information. Participants may also ask questions of site study personnel using email. There are risks associated with email communication, and these risks increase when emails are sent without an encryption service. Risks of sending or receiving unencrypted emails include, but are not limited to:
  - Others can intercept messages
  - If messages are sent or received on an employer-owned device, the employer may have the right to save and read the messages. The internet or cell-phone provider may also have the right to save and read email messages

- A copy of the message may be saved on a device or computer system, even if it is deleted
- If an email address is not typed correctly, it can be sent to the wrong person
- Emails can spread computer viruses
- Others may be able to access messages on devices that were lost, stolen, or thrown away
- If a participant changes emails without notifying site study personnel, they may miss communications.

Participants will be encouraged to report any adverse effects occurring during the duration of the study to the study point of contact.

PSC does not provide compensation for research-related injuries and will not reimburse or pay medical expenses for the treatment of research-related injuries.

Although there is little chance for a study-related emergency, the site PI and site study personnel are required to follow institutional standard operating procedures for obtaining emergency care or treatment for adverse effects requiring such. This study has adequate personnel and equipment to respond to expected adverse effects, and maintains working knowledge of the nearest treatment facilities available to patients enrolled into this study.

## Potential Benefits

Two levels of benefit will be described to participants:

1. Benefit to Science: Results from this study will directly benefit the applied science in ASD. Understanding if the scientific design principles of CICADAS drive superior outcomes to current evidence based treatments will provide considerable insight to scientists and clinicians working in ASD.
2. Benefit to Participants: This study has the potential to directly benefit the participant, in terms of improved social functioning. We will emphasize that this is the level of benefit that is most speculative in this study, and that potential participants in any randomized controlled trial should join if the benefits to participants like them and to science from the overall trial results are compelling to them, and should not expect that the trial provides treatment benefits as such.

## Study Personnel

Key study personnel at PSC include:

- Principal Investigator ([name]): responsible for the overall design of the study protocol and data analysis plan as well as the eventual publication of the result (with input and authorship from all investigators. She is also responsible for the execution of the study protocol, and coordinating activities with all PSC and UMN staff participating in the trial. Additionally, [name] will monitor, flag and/or remove inappropriate content on the Zoom chat and report and discuss the content with the appropriate team members, including the PEERS clinician(s).
- Sponsor Study Coordinator is responsible for assisting the PI with the execution of the study protocol and for data management. The sponsor study coordinator will also be responsible for monitoring all submitted data for consistency and integrity, monitoring, flagging, removing and/or discussing the Zoom chat content with the appropriate team members, including other PEERS clinician(s). Additionally, they will responsible for discussing all qualifying criteria with site study personnel, leading virtual training sessions, and holding meetings with the site study personnel. The sponsor study coordinator will be responsible for ensuring that the site meets regulatory compliance requirements and executes the protocol, as IRB approved.

[name] and research staff at PSC disclose a conflict of interest: all are paid employees of PSC and shareholders, and could benefit if this intervention for ASD is shown to be an effective treatment in this trial.

This conflict will be mitigated by ensuring that the complete investigator team, including [name], and other PSC study personnel have joint and overlapping responsibility for the design of the protocol, the execution of the protocol, the *a priori* design of the data analysis plan, the execution of the data analysis plan, the interpretation of the study results, and the authorship of publications emerging from the study. In addition, this conflict of interest will be disclosed to all study participants, and through standard mechanisms for all publications.

Key study personnel at UMN include:

- Principal Investigator ([name]): responsible for the overall execution of the study protocol at the Study Site, including overseeing participant recruitment, enrollment and intervention delivery in conjunction with the site study team for this clinical trial. She will provide support and coordinate activities between PSC and UMN staff participating in the trial. She will be involved in the data analysis as well as the eventual publication of the result (with input and authorship from all investigators). Additionally, she will ensure that the site meets regulatory compliance requirements and executes the protocol, as IRB approved. [name] will be blinded to participant randomization assignments.

- Site Study Coordinator is responsible for assisting the Site PI with the execution of the study protocol, recruiting, screening, enrolling and monitoring participant progress when active in the study. They will also be responsible for entering data into REDCap, reviewing data for consistency and integrity, reconciling data queries, and may randomize participants. Site study coordinator may serve as a back-up PEERS clinician and may be responsible for removing and/or discussing the Zoom chat content with the appropriate team members, including other PEERS Clinician(s) and the Posit Science research team. Additionally, they will assist in ensuring that the Site meets regulatory compliance requirements and executes the protocol, as IRB approved.
- Site Clinical Assessor will serve as the blinded psychometrician and clinical rater. They will conduct eligibility and clinical assessments with participants and will be blinded to their randomization assignment.
- PEERS clinician will lead the PEERS group sessions. For remote group sessions, they will monitor the Zoom forum and may be responsible for removing and/or discussing the Zoom chat content with the appropriate team.

## Blinding

Un-blinded Roles: PEERS clinicians and the site study coordinator are un-blinded in order to lead group sessions and support for participants using their assigned programs. They will be distinct from staff administering and scoring assessments. Additionally, designated personnel that are un-blinded may not participate in the assessment and evaluation at Mid-Intervention (V3) or Post-Intervention (V4) assessment visits of study participants.

Blinded Roles: All site staff responsible for the administration and scoring of participant assessments visits conducted after randomization will remain blinded to participant treatment. The Site Principal Investigator will be required to complete a Delegation of Authority Form, indicating which activities individual research team members will be authorized to complete. Principal Investigators will also remain blinded.

Depending upon the extent to which they are responsible for data collection and/or entry, *site study coordinators* may or may not remain un-blinded to participant treatment. This will be clarified on a site-by-site basis and will be noted on the Site Principal Investigator Delegation of Authority Form.

To prevent un-blinding, the following will occur:

1. The treatment arms will be identified as “Arm A, Arm B, and Arm C.”

2. Participants will be reminded not to discuss details related to treatment with blinded psychometricians and/or clinical evaluators during the informed consent process as well as prior to initiation, and at the conclusion of, each assessment visit;
3. Site study personnel will be instructed to not discuss details of either treatment arm during open participant groups or forums outside of the assigned group sessions or cohort discussions;
4. Site study personnel will be required execute the protocol in a manner that minimizes the possibility of accidental un-blinding of psychometricians or clinical evaluators (e.g. unintended viewing of treatment sessions);

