#### *Application Security*

**CICADAS and Active Control apps:** All usage and progress data collected through the CICADAS and Active Control applications are encrypted then transmitted to a central server. Data is encrypted in transit and at rest, and access is limited and audited. Data collected through the platform will not include geographic information. IP address data is stored only in memory and in request logs, and is used for technical support and troubleshooting, but not persisted with the participant's data. However, data as it relates to dates that assessments are completed is collected and stored. On the server, the data are available for review by the unblinded members including, site study coordinator, Posit Science study team, and/or other

study personnel, through a secure web portal. The study team in particular will use the secure web portal to regularly check on usage and progress of each active participant to customize their weekly phone/in-person to provide helpful guidance and coaching.

**Zoom:** This platform allows participants to communicate with others via the app without having to share their full name, mobile phone number or email to do so. Participants will choose whether to use their first name or an alias. In order to access the Zoom meeting, participants will be required to enter a passcode for their specific meeting. Once the participants enter the meeting, they will be operating within the Zoom HIPAA-compliant digital environment, and data that are produced, transmitted, and shared among users will be exclusively visible/readable to other participants and study staff. These data will include personally identifiable information—such as faces, first names or aliases, biographical and medical information—similar to what happens during all in-person group therapy sessions. Participants will be aware that the research team will have access to the group chat history and will be monitoring its contents throughout the intervention periods. As such, participants are informed that any personally identifying information voluntarily shared on this platform will be viewed by study staff. More information about how Zoom protects privacy can be found here:

<https://zoom.us/en-us/trust/privacy.html>

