### **Reporting of Serious Adverse Effects & Unanticipated Device Effects**

The CICADAS protocol has minimal risk, and previous studies of similar approaches in psychiatric populations have not reported significant adverse events arising from intervention

and program use. Additionally, computerized treatment studies using Posit Science software in healthy aging, schizophrenia, and TBI have never reported adverse events attributable to study activities. Nonetheless, to follow best practices for treatment trials in medical indications, we will employ a central Medical Research Monitor to review all unanticipated problems involving risk to participants, serious adverse events, and any participant deaths associated with the protocol, and provide an unbiased written report of the event within ten calendar days. The Medical Research Monitor will comment on the outcomes of the adverse event and relationship of the event to the protocol or test article. The Medical Research Monitor will also indicate whether they concur with the details of the report provided by the study staff member. Reports for events determined by designated study personnel, i.e. Medical Research Monitor, to be possibly or definitely related to participation, and reports of events resulting in death will be promptly forwarded to Western IRB. Further, serious adverse events attributable to study activities and/or the intervention and/or program use, will be documented and reported immediately to the Western IRB. An event that is serious must be recorded on the case record and requires expeditious handling to comply with regulatory requirements. In the event that a patient becomes ill or injured as a direct result of participation in the project, necessary medical care will be made available.

The site study coordinator and PEERS clinician will ask about any deterioration in symptoms during each contact with participants, and will be alert to any volunteered episodes of suicidality. All events of this nature will be documented on a standardized form and will be classified by the PI to their degree of seriousness and their relationship to the study protocol. Participants will be referred to appropriate clinical care should there be any concerns for safety or increasing symptoms. If deemed clinically necessary, the PI may elect to remove participants from the study if they find that it is no longer in the participant's best interests to continue participation in the study.

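### The protocol says Principal Investigators stay blinded, but the sponsor PI's chat-moderation duty, and probable portal access, can reveal treatment arm

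*Protocol*

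**What the plan says.** **Blinding claim.** The protocol's Blinding section states "Principal Investigators will also remain blinded", in the plural and without exception. The un-blinded roles it names are limited: "PEERS clinicians and the site study coordinator are un-blinded in order to lead group sessions". No sponsor staff are listed there.

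**Sponsor PI's duties.** In Study Personnel, the sponsor PI's role description says this person "will monitor, flag and/or remove inappropriate content on the Zoom chat" and discusses the content with other team members, including the PEERS clinicians. It does not mention blinding. The site PI's role description does: this person "will be blinded to participant randomization assignments".

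**Portal.** Application Security says that, on the server, "the data are available for review by the unblinded members including, site study coordinator, Posit Science study team" and other study personnel. It adds: "The study team in particular will use the secure web portal to regularly check on usage and progress of each active participant".

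**Adverse events.** The section on reporting serious adverse effects says that symptom deterioration and suicidality events found by the site coordinator or PEERS clinician are "classified by the PI to their degree of seriousness and their relationship to the study protocol". It does not say which PI. For forwarding reports to the IRB, the Research Monitor section lets either the PI or the Research Monitor find an event related, whereas the serious-adverse-effects section names the Medical Research Monitor. The SAP lists reported side effects among the primary outcomes and expects no adverse events from use of the program.

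**The concern.** The Blinding section and the role assignments do not fit together for the sponsor PI. Someone who follows the PEERS chat sees who is attending PEERS, and in this design attendance in a given period depends on arm. Someone with participant-level usage data also sees which app is in use.

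Blinded assessors protect the scoring of outcomes, but they do not protect judgements made by a PI. The one that matters most here is whether an adverse event is related to the study. Against an expectation of zero, a single attribution changes the finding. Study Personnel discloses that the sponsor PI and the sponsor's research staff are paid employees and shareholders who could gain from a favourable result. If that PI is not in fact blinded, a report calling the PIs blinded would claim a protection that the protocol's own assignments contradict.

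**Working it through.** The plan gives no figure to reproduce. The check sets the sections side by side and makes one hand count.

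**1. Whom the claim covers.** Study Personnel lists two Principal Investigators, one at the sponsor and one at the University of Minnesota, which is the only study site named. Modifications to the Protocol also speaks of PIs in the plural. The plural in the Blinding section therefore most naturally includes the sponsor PI.

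**2. What the chat can show.** Inputs from General Study Design and Treatment Arms: 16 completers per arm, 48 in all. Arms B and C attend PEERS in the first 16 weeks; Arm A does not. (The SAP's Statistical Plan describes the second 16 weeks differently for Arm A, but this step needs only the first period.) Assumptions: all groups meet remotely and every chat name can be linked to a participant.

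- Arm A is identified by absence: 16 × 1 = 16 correct.
- B and C cannot be told apart, because the two apps are made to look alike: (16 + 16) × 1/2 = 16 expected correct.
- Total: 16 + 16 = 32 of 48, or 67%.
- Under full blinding: 48 × 1/3 = 16 of 48, or 33%.

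If no names can be linked, or all groups meet in person, the chat adds nothing and the count stays at 16. The range is therefore 16 to 32 of 48.

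**3. What the portal can show.** Assume that a participant's record shows which app produced it. That separates Arm C (control app) from Arms A and B (CICADAS). Alone it gives 16 + 32 × 1/2 = 32 of 48. Combined with linkable PEERS attendance it separates all three arms: 48 of 48. This step applies to the sponsor PI only if that person belongs to the Posit Science study team for portal purposes. Study Personnel points that way, since the sponsor PI comes first among the sponsor's key personnel and is responsible for executing the protocol. The Recruitment section, however, mentions the Posit Science study team and the PI side by side, as if distinct.

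**4. Application Security against Blinding.** One section calls the Posit Science study team un-blinded; the other omits it from the un-blinded roles. They disagree whatever access the sponsor PI has.

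**5. Listed safeguards.** The Blinding section gives four measures: neutral arm labels, reminders to participants, limits on what site personnel discuss, and care to avoid un-blinding psychometricians and clinical evaluators. None restricts the sponsor PI's view of the chat or portal.

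**6. Who judges relatedness.** The Research Monitor reviews serious events, unanticipated problems involving risk, and deaths. Non-serious events fall outside that review but can still count as reported side effects. For these the protocol names only the PI, unspecified, and the sentence concerns relationship to the study protocol.

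**The case against.** The strongest reply is that the blinding sentence was never meant for the sponsor PI. It closes a paragraph about site staff and the Site PI, the next paragraph speaks of arrangements site by site, and only the site PI's role description promises blinding. This narrower reading is possible, but less natural with one named site and two named PIs. If it is right, the protocol says nothing about the sponsor PI's status, and the disagreement over the Posit Science team remains.

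Second, a reader might infer that the sponsor PI can identify every participant's arm. The documents do not support this as a flat statement. Aliases are allowed, groups may meet in person, the chat never separates B from C, and the sponsor PI's portal access is inferred. This objection stands, which is why the counts above are conditional.

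Third, a reader might infer that a financially interested PI decides the adverse-event outcome. That is not shown either. The site coordinator and PEERS clinician gather these events, so the PI who classifies them may well be the blinded site PI. The Research Monitor already states whether it concurs on serious events. The SAP describes the outcome as a raw score of reported side effects, with zero program-related events as an expectation; it defines no PI-adjudicated endpoint. What remains is that the protocol leaves the classifier unnamed and non-serious events without independent review.

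Finally, Study Personnel offers mitigation of the conflict of interest: joint and overlapping responsibility for design, analysis and interpretation, together with disclosure. That is relevant, but it does not establish blinding.

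**Conclusion.** The point holds as an internal contradiction with limited reach. The protocol declares its Principal Investigators blinded and gives one of them a task that can reveal arm. From the chat alone the size is between 16 (no information) and 32 of 48 expected correct guesses, depending on remote delivery and linkable names. It reaches 48 of 48 only if the sponsor PI also sees participant-level portal data.

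The consequence is possible un-blinded attribution of non-serious events by an interested person, if the unspecified PI is the sponsor PI. It would be wrong to read this as bias in the efficacy measures through scoring: administration and scoring of post-randomization assessments are assigned to blinded staff. Nor is a between-arm contrast of side effects at risk, because the SAP analyses that outcome in the CICADAS-users population only. The matter should be corrected, but it does not undermine the feasibility design.

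**What to change.** - Remove Zoom chat moderation from the sponsor PI's role. The sponsor study coordinator and the PEERS clinician already have this duty.
- Bar the sponsor PI from participant-level portal data until database lock, and say so in Application Security.
- List the other Posit Science study team members as un-blinded in the Blinding section, so that the two sections agree.
- Name the blinded site PI as the person who classifies relatedness, in both the Research Monitor and serious-adverse-effects sections. Leave the Research Monitor's review of serious events unchanged.

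If the sponsor needs that PI to keep the chat or portal role, withdraw the blinding claim for the sponsor PI and do not report that person as blinded.

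The cost is wording changes and one access-permission change. No extra staff, data or sample size are needed.
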